8.2. Laboratory Evaluations

8.2.1. Clinical Laboratory Evaluations

Serum β HCG pregnancy tests will be done at the screening visit for all females of childbearing potential and processed locally by the site laboratory. A urine pregnancy test will be performed within 24 hours prior to each study vaccination on all females of childbearing potential. Urine will be collected in a sterile urine cup for processing by research staff using a CLIA waived urine pregnancy test kit. Results must be negative and known prior to randomization on Day 1 and prior to administration of study vaccination on Day 8.

Venous blood will be collected prior to the first study vaccination on day 1 for high resolution HLA typing for Class 1 (A, B, and C locus) testing.

Clinical screening laboratory tests will be performed at the screening visit and processed by the local (clinical) laboratory. Parameters to be evaluated to confirm trial eligibility as per [Section 5.1](#), include the following:

- Hematology: WBC, Hgb, platelet count, ANC, and HgbA1c.
- Biochemistry: Creatinine, sodium, potassium, albumin, total protein and ALT. BUN will be done if creatinine is above the normal range.
- Serum serology testing for HIV – 1/2 antibody, HCV antibody, and HBsAg.
- Clotting: PT and PTT
- Urinalysis will be done to test for urine protein via dipstick in the clinic. Clean-catch, mid-stream, urine specimen will be collected in a sterile urine cup.
- Urine test for opiates: A clean-catch, mid-stream urine specimen will be collected in a sterile urine cup and transported to the clinical laboratory for processing and examination.

Clinical safety labs will be performed on Day 1, 8, 15, 29, and 36. If they are abnormal, they will be assessed, documented, reported, and followed until the lab returns to the subject's baseline value or has stabilized. Clinical safety laboratory parameters to be evaluated will include WBC, Hgb, platelet count, ANC, sodium, potassium, creatinine and ALT. BUN will be obtained only if creatinine is above the normal range. These evaluations will be performed by the local (clinical) laboratory. Venous blood will be collected for safety laboratory evaluations and performed by the local (clinical) laboratory for early termination visits or unscheduled visits occurring within 28 days post second study vaccination.

8.2.2. Special Assays or Procedures

Immunogenicity testing will include the following (post first vaccination):

- Humoral responses by ELISA and ADCC at Day 1, 8, 15, 22, 29 and 36.
- Humoral response by EBOV GP Neut at Day 1, 8 and 15.
- Cell-mediated immunity assays (EBOV GP T cell response) at Day 1, 8, 15, 22, and 36.
- Cell-mediated immunity assays (ChAd3 vector T cell response) at Day 1, 8, 15, 22 and 36.
- Plasmablasts (5), BCR repertoire analysis (11), CD8 tetramer staining and activation marker analysis at Day 1, 8 and 15.
- Cytokine/chemokine measurement at Day 1, 2, 3, 4, 6, 8, 9, and 15.
- Transcriptomics/Gene expression PBMCs at Day 1, 2, 3, 4, 6, 8, 9 and 15.

- Characterization of antigen-specific BCR as measured by yeast display on day 36.

Venous blood samples will also be collected for future use. 8 mL will be collected on Day 1, 8, 15, 22 and 36 post first vaccination. 42 ml will be collected on Day 182 post first vaccination. Collection of future use samples is a condition of participation in this study.

The volume (ml) of venous blood to be collected for immunogenicity assays and future research is presented in [Table 2](#).

Table 2: Blood Volumes (ml)

Study Visit (V)	0	1	2	3	4	5	6	7	8	9	10	11	12	13	14	US	ED
Study Day (from Vaccine 1)	<-29	1	2	3	4	6	8	9	15	22	29	36	76	106	182		
Screening Lab	14.2																
Clinical Safety Evaluations		6.5					6.5		6.5		6.5	6.5				6.5^	6.5^
High Resolution HLA typing for Class 1 (A, B, C locus)		6.0															
Humoral response – ELISA (Op 2)																	
Humoral response – ADCC (Op 7)		10.0						10.0		10.0	10.0						10.0^
Humoral Response, EBOV GP Neut Antibody (Op7a)																	
EBOV GP T cell responses (Op 3)		24.0						24.0		24.0	24.0		24.0				
ChAd3 vector T cell responses (Op 4)																	
Plasmablasts (Op 5, 11)		32.0					32.0		32.0								
Cd8 Tetramer Staining (Op 9)			8.0														8.0*
Activation Marker Analysis (Op 10)								8.0		8.0							
Exploratory cytokine/chemokine (Op 6)		5.0	5.0	5.0	5.0	5.0	5.0	5.0	5.0								
Transcriptomics PMBCs (Op 8)		16.0	16.0	16.0	16.0	16.0	16.0	16.0	16.0								
Yeast Display													16.0				
Future Use		8.0					8.0		8.0	8.0		8.0		42.0			
Total per visit	14.2	115.5	21.0	21.0	21.0	21.0	109.5	21.0	109.5	42.0	16.5	64.5	0.0	0.0	42.0	6.5	14.5-24.5
Running Total	14.2	129.7	150.7	171.7	192.7	213.7	323.2	344.2	453.7	495.7	512.2	576.7	576.7	576.7	618.7	N/A	N/A

[^] to be collected if visit occurs prior to or on Day 36 (post first vaccination)

* to be collected if visit occurs prior to or on Day 15 (post first vaccination)

8.2.3. Specimen Preparation, Handling, and Shipping

8.2.3.1. Instructions for Specimen Preparation, Handling, and Storage

Instructions for specimen preparation, handling, and storage are included in the protocol-specific MOP as appropriate.

8.2.3.2. Specimen Shipment

Specimen shipment will occur when all specimens are available following all applicable International Air Transport Association (IATA) requirements and according to the specifics for storage temperature and documentation as detailed in the local (clinical) laboratory manual and protocol-specific MOP as appropriate.

All specimens for clinical screening and safety laboratory evaluations will be transported from the participating VTEU site to the local (clinical) laboratory.

Specimens for cellular assays will be transported from the participating VTEU site to the local (research) laboratory.

Specimens for antibody assays will be shipped from the participating VTEU site to the Clinical Materials Services.

Further instructions for specimen shipment are included in the local (clinical) laboratory manual and protocol-specific MOP, as appropriate.

9 ASSESSMENT OF SAFETY

9.1. Specification of Safety Parameters

Safety will be assessed by the occurrence of:

1. Serious adverse events, and MAAEs occurring from the time of study vaccination through approximately 6 months after the first study vaccination.
2. Solicited Adverse Events – reactogenicity events occurring from the time of study vaccination through 7 days after each study vaccination:
 - a) Local AEs including pain, tenderness, erythema (redness), induration (hardness/swelling), ecchymosis (bruising) and pruritis (itching).
 - b) Systemic AEs including fever, feverishness (chills, shivering, sweating), fatigue (tiredness), malaise (general unwell feeling), myalgia (body aches/muscular pain), nausea, loss of appetite and headache.
3. Clinical safety laboratory adverse events occurring from the time of study vaccination through approximately 28 days after the second vaccination. Parameters to be evaluated include WBC, Hgb, platelet count, ANC, sodium, potassium, Creatinine, BUN (BUN will be obtained only if creatinine is above the normal range), and ALT.
4. Unsolicited Adverse Events – study vaccine-related non-serious adverse events occurring from the time of study vaccination through approximately 28 days after the second study vaccination.

9.2. Methods and Timing for Assessing, Recording, and Analyzing Safety Parameters

9.2.1. Adverse Events

Adverse Event: ICH E6 defines an AE as any untoward medical occurrence in a patient or clinical investigation subject administered a pharmaceutical product regardless of its causal relationship to the study treatment. FDA defines an AE as any untoward medical occurrence associated with the use of a drug in humans, whether or not considered drug related.

An AE can therefore be any unfavorable and unintended sign (including an abnormal laboratory finding), symptom, or disease temporally associated with the use of medicinal (investigational) product. The occurrence of an AE may come to the attention of study personnel during study visits and interviews of a study recipient presenting for medical care, or upon review by a study monitor.

AEs, including solicited local (injection site) and systemic (subjective and quantitative) reactions, will be captured on the appropriate data collection form and eCRF. Information to be collected for unsolicited non-serious AEs includes event description, date of onset, assessment of severity, relationship to study product and alternate etiology (assessed only by those with the training and authority to make a diagnosis and listed on the Form FDA 1572 as an investigator), date of resolution, seriousness and outcome. AEs occurring during the trial collection and reporting period will be documented appropriately regardless of relationship. AEs will be followed through resolution.

Any medical condition that is present at the time that the subject is screened will be considered as baseline and not reported as an AE. However, if the severity of any pre-existing medical condition increases, it should be recorded as an AE.

All AEs must be graded for severity and relationship to study product (see definitions). Adverse events characterized as intermittent require documentation of onset and duration of each episode. The start and stop date of each reported AE will be recorded on the appropriate data collection form and eCRF.

Severity of Event: AEs will be assessed by the investigator using a protocol-defined grading system (toxicity table included as an appendix). For events not included in the protocol-defined grading system, the following guidelines will be used to quantify severity:

- **Mild (Grade 1):** Events require minimal or no treatment and do not interfere with the subject's daily activities.
- **Moderate (Grade 2):** Events result in a low level of inconvenience or concern with therapeutic measures. Moderate events may cause some interference with functioning and daily activities.
- **Severe (Grade 3):** Events interrupt the subject's daily activities and may require systemic drug therapy or other treatment. Severe events are usually incapacitating.

Changes in the severity of an AE should be documented to allow an assessment of the duration of the event at each level of intensity to be performed. Adverse events characterized as intermittent require documentation of onset and duration of each episode.

Relationship to Study Products: The assessment of the relationship of an AE to the administration of study product is made only by those with the training and authority to make a diagnosis and listed on the Form FDA 1572 as an investigator based on all available information at the time of the completion of the eCRF. Whether the AE is related or not, is not a factor in determining what is or is not reported in this trial. If there is any doubt as to whether a clinical observation is an AE, the event should be reported.

In a clinical trial, the study product must always be suspect. To help assess, the following guidelines are used.

- Related – There is a reasonable possibility that the study product caused the adverse event. Reasonable possibility means that there is evidence to suggest a causal relationship between the study product and the adverse event.
- Not Related – There is not a reasonable possibility that the administration of the study product caused the event.

Medically Attended Adverse Event (MAAE): For each unsolicited AE experienced, the subject will be asked if he/she had received medical attention, defined as hospitalization, an emergency room visit, or an otherwise unscheduled visit to or from medical personnel for any reason. AEs characterized by such unscheduled medical care will be designated as MAAEs.

9.2.2. Reactogenicity

Reactogenicity events are AEs that are common and known to occur following administration of this type of study vaccine. The following Toxicity Grading Scales will be used to grade solicited local (injection site) and systemic (subjective and quantitative) reactions:

Table 3: Local (Injection Site) Reactogenicity Grading

Local (Injection Site) Reaction	Mild (Grade 1)	Moderate (Grade 2)	Severe (Grade 3)
Pain – experienced without touching the injection site (spontaneous discomfort)	Subject is aware of pain, but it does not interfere with daily activity, and no pain medication is taken	Subject is aware of pain; there is interference with daily activity or it requires repeated use of a non-narcotic pain reliever for >24 hours	Subject is aware of pain, and it prevents daily activity or requires any use of a prescription medication.
Tenderness – hurts only when injection site is touched or the arm is moved	The area immediately surrounding the injection site hurts only when touched or with arm motion, and it does not interfere with daily activity	The area immediately surrounding the injection site hurts when touched or with arm motion, and it interferes with daily activity	The area immediately surrounding the injection site hurts when touched or with arm motion, and it prevents daily activity
Erythema (Redness)*	Does not interfere with daily activity	Interferes with daily activity	Prevents daily activity
Induration (Hardness/Swelling)*	Does not interfere with daily activity	Interferes with daily activity	Prevents daily activity

Local (Injection Site) Reaction	Mild (Grade 1)	Moderate (Grade 2)	Severe (Grade 3)
Ecchymosis (Bruising)*	Does not interfere with daily activity	Interferes with daily activity	Prevents daily activity
Pruritus (Itching)	Does not interfere with daily activity	Interferes with daily activity	Prevents daily activity

* Will also be measured in mm but size will not be used as halting criteria.

Ecchymosis (bruising), erythema (redness) and induration (hardness)/swelling as analyzed by measurement will be graded as follows:

Table 4: Local (Injection Site) Reactogenicity Measurements

Local (Injection Site) Reaction	Small	Medium	Large
Ecchymosis (Bruising)*	<20 mm	20 mm – 50 mm	>50 mm
Erythema (Redness)*	<20 mm	20 mm – 50 mm	>50 mm
Induration (Hardness)/Swelling*	<20 mm	20 mm – 50 mm	>50 mm

* Will not be used as halting criteria.

Table 5: Subjective Systemic Reactogenicity Grading

Systemic (Subjective)	Mild (Grade 1)	Moderate (Grade 2)	Severe (Grade 3)
Feverishness (chills/shivering/sweating)	noticeable but does not interfere with daily activity	interferes with daily activity	Significant interference, prevents daily activity
Malaise (General Unwell Feeling)	noticeable but does not interfere with daily activity	interferes with daily activity	Significant interference, prevents daily activity
Fatigue (Tiredness)	noticeable but does not interfere with daily activity	interferes with daily activity	Significant interference, prevents daily activity
Myalgia (Body Aches/Muscular Pain)*	noticeable but does not interfere with daily activity	interferes with daily activity	Significant interference, prevents daily activity
Headache	noticeable but does not interfere with daily activity	Any use of pain reliever or interferes with daily activity	Significant interference, prevents daily activity, or requires any use of a prescription medication

Systemic (Subjective)	Mild (Grade 1)	Moderate (Grade 2)	Severe (Grade 3)
Nausea	noticeable but does not interfere with daily activity	interferes with daily activity	Significant interference, prevents daily activity
Loss of Appetite	noticeable but does not interfere with daily activity	interferes with daily activity	Significant interference, prevents daily activity

* Not at injection site.

Oral temperature[#] will be graded as follows:

Table 6: Quantitative Systemic Reactogenicity Grading

Systemic (Quantitative)	Mild (Grade 1)	Moderate (Grade 2)	Severe (Grade 3)
Fever* - oral [†]	37.8°C – 38.4°C 100.00°F – 101.1°F	38.5°C – 38.9°C 101.2°F – 102.0°F	>38.9°C >102.0°F

Oral temperature assessed on Day 1 prior to study vaccination will be considered as baseline.

* A fever can be considered not related to the study product if an alternative etiology can be documented.

† Subjects must not eat or drink anything hot or cold, or smoke within 10 minutes prior to taking oral temperature.

Pulse and blood pressure[#] will be graded as follows:

Table 7: Blood Pressure and Pulse Grading

Physiologic Parameter	Mild (Grade 1)	Moderate (Grade 2)	Severe (Grade 3)
Bradycardia - beats per minute	45-46	40 – 44	<40
Tachycardia - beats per minute	106 – 130	131 – 155	>155
Hypotension (systolic) mmHg	80 – 84	75 – 79	<75
Hypotension (diastolic) mmHg	50 – 54	45 – 49	<45
Hypertension (systolic) mmHg	151 – 155	156 – 160	>160
Hypertension (diastolic) mmHg	96 – 100	101 – 105	>105

Pulse and blood pressure assessed on Day 1 prior to study vaccination will be considered as baseline.

Clinical safety laboratory results will be graded as follows:

Table 8: Clinical Safety Laboratory Adverse Event Grading (Hematology)

Hematology	Clinical Laboratory Reference Range	Mild (Grade 1)	Moderate (Grade 2)	Severe (Grade 3)
WBC K/mcL (Decrease, 18 to <21 years)	4.5 – 13.0	2.5 – 4.4	1.5 – 2.4	<1.5
WBC K/mcL (Decrease, \geq 21 years)	4.5 – 11.0	2.5 – 4.4	1.5 – 2.4	<1.5
WBC K/mcL (Increase 18 to <21 years)	4.5 – 13.0	13.1 – 15.0	15.1 – 20.0	>20.0
WBC K/mcL (Increase \geq 21 years)	4.5 – 11.0	11.1 – 15.0	15.1 – 20.0	>20.0
Hgb g/dL (Decrease) (Female)	11.7 – 15.7	10.1 – 11.6	8.5 – 10	<8.5
Hgb g/dL (Decrease) (Male)	13.3 – 17.7	11.0 – 13.2	9.5 – 10.9	<9.5
Platelet count K/mcL (Decrease)	135 - 466	125 – 134	100 – 124	<100
Platelet count K/mcL (Increase)	135 - 466	467 - 517	518 – 750	>750
Absolute Neutrophil Count, K/mcL* (18 to < 21 years)	1.80 – 8.00	1.5-<1.8	1.0-<1.5	<1.0
Absolute Neutrophil Count, K/mcL* (\geq 21 years)	1.80 – 7.70	1.5-<1.8	1.0-<1.5	<1.0
Absolute Neutrophil Count, K/mcL - Benign Ethnic Neutropenia*	\geq 0.8	0.6 – 0.7	0.4 -- 0.5	< 0.4

* ANC for subjects that are of African American and Middle Eastern descent may have values as low as 0.8 x K/mcL.

Subjects of this descent must have an ANC \geq 0.8 K/mcL to be eligible to participate in the study if all other study criteria are met.

Table 9: Clinical Safety Laboratory Adverse Event Grading (Chemistry)

Chemistry	Clinical Laboratory Reference Range	Mild (Grade 1)	Moderate (Grade 2)	Severe (Grade 3)
ALT unit/L (Increase)	\leq 49	50 - 123	124 - 245	> 245
Creatinine mg/dL (Increase - Female)	0.50–0.80	0.81–1.70	1.71–2.00	>2.00
Creatinine mg/dL (Increase - Male)	0.60–1.10	1.11 – 1.70	1.71 – 2.00	>2.00
Sodium, low, mmol/L	136 – 145	130 - 135	123-129	<123
Sodium, high, mmol/L	136 - 145	146 - 150	151-157	>157
Potassium, high, mmol/L	3.5 – 5.1	5.2 - 6.0	6.1-6.5	>6.5
Potassium, low, mmol/L	3.5 – 5.1	3.0 - 3.4	2.5-2.9	<2.5
Blood Urea Nitrogen (BUN) mg/dL	9.00 – 23.00	24 - 26	27-31	>31

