6.6. Concomitant Medications/Treatments

Administration of any medications, therapies, or vaccines will be recorded on the appropriate data collection form. Concomitant medications will include all current medications and medications taken within 60 days prior to signing the informed consent form through approximately 28 days after the second study vaccination or early termination (if prior to 28 days

after the second study vaccination), whichever occurs first. Assessment of study eligibility will include a review of all permitted and prohibited medications per the Subject Inclusion and Exclusion Criteria (see [Section 5](#)). Medications reported in the electronic case report form (eCRF) are limited to those taken within 30 days prior to study vaccination through approximately 28 days after the second study vaccination. Prescription and over-the-counter drugs will be included as well as herbals, vitamins, and supplements. In addition, receipt of non-study vaccines will be solicited through approximately 28 days after the second study vaccination, and reported in the eCRF.

Use of new medication should prompt evaluation for the occurrence of an AE or worsening of a pre-existing medical condition.

Medications that might interfere with the evaluation of the investigational product(s) should not be used from time of study vaccination through 28 days post the second vaccination unless clinically indicated as part of the subject's health care. Medications in this category include the prohibited medications per the Subject Exclusion Criteria (see [Section 5.2](#)). In addition, the site principal investigator or appropriate sub-investigator may identify other medications that should not be used due to a risk to subject safety or assessment of reactogenicity and immunogenicity. Use of medications as prophylaxis prior to study vaccination is prohibited. There are no known drug-vaccine interactions with the study vaccine and subjects are not being asked to discontinue current medications not listed in the exclusion criteria. In the event medical conditions dictate use of medications, subjects are encouraged to obtain adequate care, comply with the course of therapy as prescribed by their physician and inform the site as soon as practicable. Details of all medications taken during the medication reporting period for this study (date, indication, brand or generic name) will be recorded.

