11.4.2. Safety Data

Safety data will be summarized for the Safety Analysis Population. Pre-second vaccination, Study Groups 1, 2, 3 will be analyzed jointly as one study group as all three groups received the same vaccine at Day 1.

Solicited AEs will be summarized by severity for each day after each study vaccination (Days 1 through 7 days post-vaccination) and as the maximum severity over all days after each vaccination. The maximum severity of local and systemic reactions will be determined for each subject and summarized by study group following each vaccination (as well as post any vaccination) and the resulting number, percentage (observed rate) of subjects and associated exact 95% confidence interval (CI) will be summarized by severity grade (none, mild, moderate, severe) and symptom. Summaries will also be provided for any systemic symptoms, for any local symptoms, and for any systematic or local symptoms.

Vaccine-related unsolicited AEs from the first study vaccination through 28 days post second vaccination will be coded by Medical Dictionary for Regulatory Activities (MedDRA®) for preferred term and system organ class (SOC). These AEs will be summarized as number and percentage of subjects reporting at least one event in each MedDRA® preferred term and SOC, cross tabulated by severity grade (none, mild, moderate, severe). Additionally, the number, percentage (observed rate) and exact two-sided 95% CI for subjects reporting a related unsolicited AE overall, by SOC, and by preferred term will be summarized by study group.

Clinical safety laboratory AEs from the time of first study vaccination through approximately 28 days after the second vaccination will be summarized by severity grade (none, mild, moderate, severe) for each laboratory visit. In addition, the maximum severity over all post-vaccination visits will be summarized by study visit and by severity grade (none, mild, moderate, severe) using percentages and exact two-sided 95% CIs.

The number of SAEs and vaccine-related Medically Attended Adverse Events (MAAEs) through 6 months post first vaccination will be reported by detailed listings showing the event description, preferred term and SOC, relevant dates (study vaccinations and AEs), severity, vaccine-relatedness, and outcome for each event.

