9.3. Adverse Events

9.3.1. Solicited Events and Symptoms

Solicited adverse events collected 30 minutes post-vaccination (in-clinic assessment) and then daily for 7 days after each vaccination (through Day 8) will be graded on a scale of 0 (absent), 1 (mild), 2 (moderate) and 3 (severe). Local reactogenicity grading are provided in [Table 4](#) and [Table 5](#) and include:

- Pain – experienced without touching the injection site (spontaneous discomfort)
- Tenderness – hurts only when injection site is touched, or the arm is moved
- Erythema (Redness)
- Induration (Hardness/Swelling)
- Ecchymosis (Bruising)
- Pruritus (Itching)

The systemic reactogenicity grading is provided in [Table 6](#) and [Table 7](#) and includes:

- Feverishness (chills/shivering/sweating)
- Malaise (General Unwell Feeling)

- Fatigue (Tiredness)
- Myalgia (Body Aches/Muscular Pain)
- Headache
- Nausea
- Loss of Appetite
- Elevated Oral Temperature

Pre-second dose, safety events will include all safety assessments through Day 8 post-dose 1. If the second dose occurred on Day 8, Day 8 pre-second dose safety events will include memory aid assessments and in-clinical assessments that occurred prior to dose 2.

Safety data will be summarized for the Safety Analysis Population. Pre-second vaccination, Study Groups 1, 2, 3 will be analyzed jointly as one study group as all three groups received the same vaccine at Day 1.

[Table 23](#) will provide an overview of safety events by study arm and overall. Solicited AEs will be summarized using the maximum severity over all days after each vaccination overall by vaccination and symptom (subjects with mild or higher severity grading, [Table 24](#)) and by severity (none, mild, moderate, severe) and symptom ([Table 25](#)). In both cases, the resulting number, percentage (observed rate) of subjects and associated exact (Clopper-Pearson) 95% CIs by symptom, any systemic symptom, any local symptom, and any symptom (systematic or local symptom) will be provided. In addition, solicited AEs will be tabulated by severity for each day after each study vaccination (Days 1 through Day 8) following each vaccination ([Table 26](#) and [Figure 4](#)). Subject-level solicited events will be provided as shown in [Listing 10](#) and [Listing 11](#).

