	Mild	x	x.x	x	x.x	x	x.x	x	x.x	x	x.x	x	x.x	x	x.x	x	x.x	x	x.x	x	x.x
	Moderate	x	x.x	x	x.x	x	x.x	x	x.x	x	x.x	x	x.x	x	x.x	x	x.x	x	x.x	x	x.x
	Severe	x	x.x	x	x.x	x	x.x	x	x.x	x	x.x	x	x.x	x	x.x	x	x.x	x	x.x	x	x.x
Ecchymosis (Measurement grade)	None	x	x.x	x	x.x	x	x.x	x	x.x	x	x.x	x	x.x	x	x.x	x	x.x	x	x.x	x	x.x
	Mild	x	x.x	x	x.x	x	x.x	x	x.x	x	x.x	x	x.x	x	x.x	x	x.x	x	x.x	x	x.x
	Moderate	x	x.x	x	x.x	x	x.x	x	x.x	x	x.x	x	x.x	x	x.x	x	x.x	x	x.x	x	x.x
	Severe	x	x.x	x	x.x	x	x.x	x	x.x	x	x.x	x	x.x	x	x.x	x	x.x	x	x.x	x	x.x
Erythema (Functional grade)	None	x	x.x	x	x.x	x	x.x	x	x.x	x	x.x	x	x.x	x	x.x	x	x.x	x	x.x	x	x.x
	Mild	x	x.x	x	x.x	x	x.x	x	x.x	x	x.x	x	x.x	x	x.x	x	x.x	x	x.x	x	x.x
	Moderate	x	x.x	x	x.x	x	x.x	x	x.x	x	x.x	x	x.x	x	x.x	x	x.x	x	x.x	x	x.x
	Severe	x	x.x	x	x.x	x	x.x	x	x.x	x	x.x	x	x.x	x	x.x	x	x.x	x	x.x	x	x.x
Erythema (Measurement grade)	None	x	x.x	x	x.x	x	x.x	x	x.x	x	x.x	x	x.x	x	x.x	x	x.x	x	x.x	x	x.x
	Mild	x	x.x	x	x.x	x	x.x	x	x.x	x	x.x	x	x.x	x	x.x	x	x.x	x	x.x	x	x.x
	Moderate	x	x.x	x	x.x	x	x.x	x	x.x	x	x.x	x	x.x	x	x.x	x	x.x	x	x.x	x	x.x
	Severe	x	x.x	x	x.x	x	x.x	x	x.x	x	x.x	x	x.x	x	x.x	x	x.x	x	x.x	x	x.x

Table 26: Number and Percentage of Subjects Experiencing Solicited Events by Symptom, Severity, and Day (Study Arm 1, 2, and 3 (ChAd3) - Post Dose 1) (Continued)

Symptom	Severity	Pre-Dose		Post-Dose		Day 1		Day 2		Day 3		Day 4		Day 5		Day 6		Day 7		Day 8	
		n	%	n	%	n	%	n	%	n	%	n	%	n	%	n	%	n	%	n	%
Induration (Functional grade)	None	x	x.x	x	x.x	x	x.x	x	x.x	x	x.x	x	x.x	x	x.x	x	x.x	x	x.x	x	x.x
	Mild	x	x.x	x	x.x	x	x.x	x	x.x	x	x.x	x	x.x	x	x.x	x	x.x	x	x.x	x	x.x
	Moderate	x	x.x	x	x.x	x	x.x	x	x.x	x	x.x	x	x.x	x	x.x	x	x.x	x	x.x	x	x.x
	Severe	x	x.x	x	x.x	x	x.x	x	x.x	x	x.x	x	x.x	x	x.x	x	x.x	x	x.x	x	x.x
Induration (Measurement grade)	None	x	x.x	x	x.x	x	x.x	x	x.x	x	x.x	x	x.x	x	x.x	x	x.x	x	x.x	x	x.x
	Mild	x	x.x	x	x.x	x	x.x	x	x.x	x	x.x	x	x.x	x	x.x	x	x.x	x	x.x	x	x.x
	Moderate	x	x.x	x	x.x	x	x.x	x	x.x	x	x.x	x	x.x	x	x.x	x	x.x	x	x.x	x	x.x
	Severe	x	x.x	x	x.x	x	x.x	x	x.x	x	x.x	x	x.x	x	x.x	x	x.x	x	x.x	x	x.x

N = Number of subjects in the Safety Analysis Population who received the specified dose.

Severity is the maximum severity reported post dosing for each subject for each day.

*: Subjects in treatment groups that received the same study product were analyzed jointly.

Repeat this table for all three study arms post-second dose: Study Arm 1 ChAd3+Placebo Post Dose 2, Study Arm 2 ChAd3+ChAd3 Post Dose 2, and Study Arm 3 ChAd3+MVA-BN Post Dose 2.

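### Does injection-site pain treated briefly with an over-the-counter analgesic, which fits neither Grade 1 nor Grade 2, call for a change to the plan?

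*Protocol*

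**What the plan says.** Protocol Section 9.2.2, Table 3, grades spontaneous injection-site pain as follows; SAP Table 4 carries the same text.

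- Mild: "Subject is aware of pain, but it does not interfere with daily activity, and no pain medication is taken".
- Moderate: pain that interferes with activity, or that "requires repeated use of a non-narcotic pain reliever for >24 hours".
- Severe: pain that prevents activity, or any prescription drug taken for it.

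Protocol Section 9.2.1 has a general severity guide whose mild level tolerates minimal treatment, but it is introduced with "For events not included in the protocol-defined grading system, the following guidelines will be used to quantify severity". Injection-site pain is in the tables, so that guide does not formally reach it. The same section requires every adverse event to be graded. SAP Section 9.3.1 uses a 0 to 3 scale on which 0 means the symptom is absent.

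On reporting, Protocol Section 11.4.2 states that "Solicited AEs will be summarized by severity for each day after each study vaccination", and also calls for the maximum over all days. The by-day footnote to SAP Table 26 reads "Severity is the maximum severity reported post dosing for each subject for each day".

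**The concern.** A subject with a sore arm who carries on as normal and takes one over-the-counter tablet is an ordinary case, and the pain row has no cell for it. The tablet removes Grade 1 and the short duration removes Grade 2. The headache row of Protocol Table 5 shows that the omission was avoidable: its moderate level is "Any use of pain reliever or interferes with daily activity", with no duration condition.

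Daily tabulation adds a second difficulty. More than 24 hours of use cannot have accrued by the end of the first calendar day of a course. Neither document says whether that day is graded on use so far or in the light of the whole course.

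Severity of solicited local reactions is part of a primary outcome (Protocol Section 3.2.1). If raters resolve the case differently, the split between mild and moderate pain is partly a matter of rater habit. That would carry into the any-local and any-symptom severity rows of SAP Tables 25 and 26 and the local version of Figure 4.

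**Working it through.** **Step 1: enumerate the states.** Applying the three definitions to each combination gives:

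| Effect on activity | Medication | Grade met |
|---|---|---|
| None | None | 1 |
| None | Non-prescription, repeated, 25 h or 48 h | 2 |
| None | Non-prescription, repeated, 12 h or 24 h | none |
| None | Non-prescription, not repeated, any duration | none |
| None | Prescription | 3 |
| Interferes | Any | at least 2 |
| Prevents | Any | 3 |

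The gap is confined to non-interfering pain with non-prescription, non-narcotic use that is either 24 hours or less, or not repeated.

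**Step 2: what can be recorded for such an entry.** Pain is present, so 0 is excluded. Activity is not prevented and no prescription drug is used, so 3 is excluded. Grading is mandatory. The entry is therefore 1 or 2. SAP Table 24 counts mild or worse, so it is unchanged either way, as is the any-local-event count in Table 23.

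**Step 3: the first day of a longer course.** Elapsed use at the end of the first day is 24 minus the starting hour. For starts at hours 0, 8, 12 and 20 this is 24, 16, 12 and 4 hours, never more than 24. By the end of day two it is 48, 40, 36 and 28 hours, all more than 24. If each day is judged only on use so far, the first day has no defined grade and the second is Grade 2. The subject's maximum for pain is then at least 2 whatever is entered for the first day, so Table 25 cannot change. Only Table 26 and Figure 4 can.

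Nor does the wording force grading at midnight. Protocol Section 8.1 has the memory aid reviewed with the subject about eight days after each vaccination, and the SAP Listing 11 footnote says staff review diary data before reporting them in the eCRF. The full course can be known when the grade is entered.

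**Step 4: which decisions use the mild/moderate split.** The solicited-event halting rules in Protocol Section 9.5 need Grade 3 that has not fallen to a lower grade. For the second dose, Section 5.4.3 treats ongoing Grade 1 and Grade 2 events alike. Neither separates mild from moderate.

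**Step 5: size per subject.** Arms have 20 subjects, pooled to 60 after dose 1. One subject is 1/20 = 5.0 points or 1/60 = 1.7 points. Table 25 reports maximum severity with Clopper-Pearson intervals. With no events the upper limit is 1 − 0.025^(1/n), which is 16.8% for n = 20 and 6.0% for n = 60. With one event the intervals are 0.1% to 24.9% for 1/20 and 0.04% to 8.9% for 1/60. A one-subject shift is small against these widths. Table 26 has counts and percentages only, so no interval applies there.

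**The case for a change.** The best argument for acting is that nothing in either document settles the case and the available analogies conflict. The general guide leans towards mild, while the headache row makes any analgesic moderate. Two careful raters could differ on the same diary entry. The Table 26 shell gives pain only None, Mild, Moderate and Severe rows, so an ungraded report would have nowhere to go.

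The case is also likely to arise. Protocol Section 2.3.1 reports pain in 47.6% of adult recipients in the cited phase 2 studies. If that rate held here, 0.476 × 60 is about 29 subjects with pain after dose 1. Section 6.6 states that "Use of medications as prophylaxis prior to study vaccination is prohibited" and discourages drugs that might interfere with evaluation unless clinically indicated, but treating a sore arm remains possible. A convention kept only in the memory aid, eCRF or MOP would not be visible to readers of the posted plan.

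The wording gap and the conflict of analogies stand. What does not follow is a benefit from amending. SAP Sections 4.3 and 4.4.3 describe enrolment and randomisation in the past tense, so rewording the table now could not guide the raters, and recorded grades should stay as they are. A note could only report the convention used, or that there was none. A reader who wants to examine the split can set Listing 11 (pain severity by post-dose day) beside Listing 17 (each medication with start day, end day and indication) and find the entries. The 29 is a ceiling on pain reports under that assumption, not an estimate of the ambiguous subset, for which the documents give no basis.

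**Conclusion.** No change follows. The pain row contains a real but narrow drafting gap of the kind that graders fill sensibly when they complete the form. Its reach is the mild/moderate split for pain and the summaries built on it. For the first day of a longer course, its reach is the by-day displays alone. Any-pain rates, Grade 3 counts, halting and second-dose eligibility are untouched.

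The study tests no formal hypothesis (Protocol Section 11.1), and safety is reported descriptively. Post-vaccination assessors are blinded to arm (Section 5.4.2), so nothing suggests that like entries would be graded differently by arm. A more painful regimen might still produce more such entries.

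Each affected subject moves a severity percentage by 5.0 points in one arm, or 1.7 points when pooled. This conclusion assumes that the site entered a grade for every pain report, as the protocol requires, and that few subjects fall in the gap. The second assumption cannot be checked from the documents. If many did, the mild/moderate split for pain would deserve cautious reading in the CSR, but the planned analysis would be the same.
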